14.2 DERIVED EFFICACY AND SAFETY VARIABLES

The total score of each variable including MADRS, BPRS+, and CADSS at a particular visit will be calculated using $(\text{sum of nonmissing items}) \times (\text{total number of items}) / (\text{number of nonmissing items})$ only if the number of missing items is less than the specified number for each variable. Otherwise, the total score will be set to missing.

14.3 REPEATED OR UNSCHEDULED ASSESSMENTS OF SAFETY PARAMETERS

If a patient has repeated assessments before the start of DB treatment, the results from the final nonmissing assessment made before the start of the DB IP will be used as baseline. If end-of-study assessments are repeated or if unscheduled visits occur, the last nonmissing postbaseline assessment will be used as the end-of-study assessment for generating summary statistics. However, all postbaseline assessments will be used for PCS value determinations, and all assessments will be presented in the data listings.

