### **9.1.3 Safety Follow-up Period**

Patients who do not enter the RAP-MD-04 maintenance study upon completing the double-blind treatment period and patients who prematurely discontinue from the study before completing 3 weeks of double-blind treatment should enter the 1-week safety follow-up period.

Additional follow-up visits may be scheduled within 30 days, if necessary for safety reasons.

A schematic of the study design is presented in [Figure 9.1-1](#). The Schedule of Evaluations is provided in [Section 2.0](#) and detailed descriptions of each study visit can be found in [Section 9.5.6](#).

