### 9.5.2.1 *Adverse Events*

An AE is any untoward medical occurrence in a patient or clinical investigation patient administered a pharmaceutical product and which does not necessarily have to have a causal relationship with this treatment. An AE can therefore be any unfavorable and unintended sign (including an abnormal laboratory finding, for example), symptom, or disease temporally associated with the use of a medicinal product, whether or not considered related to the medicinal product (ICH-E2A).

For the purpose of the study center's data collection responsibilities, any untoward event that was reported from the time the patient signed the ICF until 30 days after the final protocol-defined study visit or the last known dose of IP (if the final visit does not occur) is to be considered an AE.

Examples of AEs are as follows:

- Changes in the general condition of the patient
- Subjective symptoms offered by or elicited from the patient
- Objective signs observed by the Investigator or other study center personnel

- All diseases that occur after signing informed consent, including any change in severity or frequency of pre-existing disease
- All clinically relevant abnormalities in laboratory values or clinically relevant physical findings that occur during the study schedule

Please note that medical procedures scheduled prior to consenting, but occurring during the study should not be captured as AEs, but should be listed in the medical history if related to a pre-existing condition.

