#### **9.5.2.1.4 Reporting Adverse Events and Serious Adverse Events**

At each visit, patients are to be queried regarding any AEs or SAEs that have occurred since the previous visit. Patients will be asked to volunteer information with a nonleading question such as, "How do you feel since your last visit?" Study center personnel will record all pertinent information in the patient's eCRF.

All AEs must be recorded on the appropriate AE reporting page of the patient's eCRF whether or not they are considered causally related to the IP.

For every AE, the Investigator must:

- Provide an assessment of the seriousness of the event (ie, is it an SAE?), as well as the severity and causal relationship
- Document all actions taken with regard to the IP
- Detail any other treatment measures taken for the AE
- Document the outcome of the AE

In addition, patients are to be reminded, as described in the ICF and in accordance with Section 9.5.2.1, to notify study center personnel of any AEs occurring during the 30-day poststudy period. Any AEs reported by the patient (or patient representative) during this period are to be recorded in original source documents. AEs are also to be recorded in the eCRF if at least one of the following conditions is met: 1) the event meets the criteria for an SAE (see Section 9.5.2.1.3 and 9.5.2.1.4), and/or 2) the event is judged by the Investigator to be potentially causally related to IP.

Any AEs that are ongoing at the time of the final protocol-defined study visit will be followed until the condition returns to prestudy status, has resolved or stabilized, or can be explained as being unrelated to the IP. If a follow-up visit is deemed necessary for appropriate safety surveillance, it will take place within 30 days of the final protocol-defined study visit.

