### **9.5.6.13 Unscheduled Visits**

Unscheduled visits can be performed if safety concerns arise and at the discretion of the Investigator. Additional examinations may be performed as necessary to ensure the safety and well-being of the patients during the study.

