14.0 DATA HANDLING CONVENTIONS

14.1 VISIT TIME WINDOWS

Table 14.1–1 presents visits assigned and the corresponding range of treatment days (window) during which an actual visit may occur for all safety analyses where baseline is the last nonmissing assessment before the first dose of DB IP in the placebo lead-in period. The visit windows used in the “change from Day 0” or “reduction from Day 0” efficacy analyses will be derived according to this table as well. Termination visit is assigned to the visit window according to the table below.

Table 14.1–1. Visit Time Windows for Change from Day 0 in Efficacy and Change from Baseline in Safety Analyses

Analysis Visit	Target Date	Analysis Window (Based on Date)
Baseline	Index0 ^a	Last record on or before Index0 ^a
Day 1	Index0 ^a +1	Index0 ^a +1
Day 4	Index0 ^a +4	[Index0 ^a +2, IndexA ^b -1]
Day 7	IndexA ^b	IndexA ^b
Day 8 ^d	IndexA ^b +1	IndexA ^b +1
Day 11	IndexA ^b +4	[IndexA ^b +2, IndexB ^c -1]
Day 14	IndexB ^c	IndexB ^c
Day 15 ^d	IndexB ^c +1	IndexB ^c +1
Day 18	IndexB ^c +4	[IndexB ^c +2, IndexB ^c +5]
Day 21 ^{de}	IndexB ^c +7	Days [IndexB ^c +6, day of final double-blind visit or Early-termination Visit occurring after IndexB ^c +5]
Day 28	IndexB ^c +14	Within the safety follow-up phase

a Index0: Date of placebo dose during the placebo lead-in period

b IndexA: Date of first randomized dose or Index0 + 7 for patients who did not receive any randomized dose

c IndexB: Date of second randomized dose or IndexA + 7 if the 2nd dosing of randomized treatment was not administered for patients who were randomized

d For analysis of parameters BPRS+ (Brief Psychiatric Rating Scale) and CADSS (Clinician Administered Dissociative States Scale), the visit windows for Days 1 and 8 will be extended to cover the next dosing day (indexA and indexB, respectively); the visit window for Day 15 will be 1 day after IndexB to Day 19; and the visit window for Day 21 will be Days 20 to the last double-blind visit, inclusively.

For efficacy analysis where baseline is defined as the last measurement prior to the first dose of randomized IP, the assigned visit and the corresponding range of treatment days (window) during which an actual visit may occur is displayed in **Table 14.1–1**. Termination visit is assigned to the visit window according to the table below.

Table 14.1–2. Visit Time Windows for Change from Baseline in Efficacy Analyses

Analysis Visit	Target Date	Analysis Window (Based on Date)

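### SAP 14.3 lets a late retest or follow-up value stand in for the Day 21/ET value in end-of-study safety summaries, with no time limit

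*SAP*

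**What the plan says.** SAP 14.3 governs repeated and unscheduled safety assessments. Its condition is "If end-of-study assessments are repeated or if unscheduled visits occur", and its consequence is that "the last nonmissing postbaseline assessment will be used as the end-of-study assessment for generating summary statistics". The text confines the chosen value neither to the double-blind period nor to any number of days after it. The next sentence adds a safeguard: "However, all postbaseline assessments will be used for PCS value determinations, and all assessments will be presented in the data listings".

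The protocol says when such extra values arise. On unscheduled visits (9.5.6.13): "Unscheduled visits can be performed if safety concerns arise and at the discretion of the Investigator". On the safety follow-up (9.1.3): "Additional follow-up visits may be scheduled within 30 days, if necessary for safety reasons". Section 9.5.2.1 lists among its examples of adverse events: "All clinically relevant abnormalities in laboratory values or clinically relevant physical findings that occur during the study schedule". Section 9.5.2.1.4 begins its follow-up rule with: "Any AEs that are ongoing at the time of the final protocol-defined study visit will be followed until the condition returns to prestudy status". That sentence goes on to allow follow-up to end when the event has resolved or stabilized, or can be explained as unrelated to the product.

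SAP Table 14.1-1 assigns safety data to visits. Its Day 21 window closes at the final double-blind or ET visit. Day 28 is a separate row whose window is "Within the safety follow-up phase".

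**The concern.** A last-value rule is harmless when the reason for a further measurement has nothing to do with the value just seen. Here the protocol ties unscheduled and extra visits to safety concerns. A patient with a worrying value at Visit 11 is therefore more likely than others to have a later one, and follow-up of an ongoing adverse event is directed towards return to prestudy status, resolution or stabilization. Under SAP 14.3 that later value becomes the patient's end-of-study value. A patient with nothing remarkable at Visit 11 keeps the Visit 11 value.

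Two things follow. The end-of-study summary no longer describes a single timepoint. And if one arm has more abnormal values, it has more substitutions, so a real difference in mean change can look smaller than it is. No hypothesis test is involved, but readers would use these summaries to judge modest drifts in laboratory, vital-sign or ECG values that stay below PCS limits, in a study meant to support a marketing application (Protocol 7.0).

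**Working it through.** The documents state no figure that depends on this rule, so there is nothing to reproduce. The check sets the rules side by side and then illustrates the direction and possible size.

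**1. Which value does each rule pick?** Take a patient whose second randomized dose falls on Day 14 (IndexB in the SAP). Visit 11 falls on Day 21 (IndexB + 7) and is the final double-blind visit. An extra safety visit follows on, say, Day 24.

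- SAP 14.1: the Day 21 window closes at the final double-blind visit, so Day 21 keeps the Visit 11 value. The Day 24 value lies outside that window and can only belong to the follow-up row.
- SAP 14.3: the end-of-study value is the Day 24 value. On the wording it could equally come from any later postbaseline record, including one at an additional visit within the 30 days that Protocol 9.1.3 allows.

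SAP 14.1 also has a rule for several values in one window: take the one closest to the target day or, if tied, the later. It is printed after the efficacy table, so its reach to safety data is not explicit. Nothing says which of 14.1 and 14.3 prevails, and two programmers could produce different end-of-study tables.

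**2. Are the two values comparable?** Protocol 9.4.7 places the last injection at Visit 8. The Day 21 value is thus already 7 days after the last dose (IndexB + 7), and the Day 28 target is 14 days after it (IndexB + 14). During follow-up no product is given and background antidepressant treatment may be changed (Protocol 9.4.7.3). Patients who enter RAP-MD-04 do not have this follow-up (Protocol 9.1). A substituted value therefore differs in time since dosing, possibly in background treatment, and in the kind of patient who has one.

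**3. Direction and size, by simulation.** All of these inputs are assumptions except the arm size, which is the SAP 12.0 figure of about 210 per arm:

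- a standardised safety measure (SD 1) with test-retest correlation 0.7;
- a true drug shift of 0.2 or 0.5 SD;
- a retest for every patient above a threshold of 1.5 or 2.0 SD, and for nobody else;
- at retest, either no recovery or full recovery of the drug shift.

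Loss = 1 − (difference using last value ÷ difference using scheduled value).

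| Shift | Recovery | Threshold | Scheduled | Last | Loss | Active arm above threshold: scheduled → last |
|---|---|---|---|---|---|---|
| 0.2 | none | 1.5 | 0.200 | 0.188 | 6.0% | 9.7% → 4.5% |
| 0.2 | none | 2.0 | 0.196 | 0.188 | 4.1% | 3.6% → 1.3% |
| 0.2 | full | 1.5 | 0.199 | 0.167 | 16.1% | 9.6% → 3.5% |
| 0.2 | full | 2.0 | 0.200 | 0.186 | 7.0% | 3.6% → 1.0% |
| 0.5 | none | 1.5 | 0.498 | 0.464 | 6.8% | 15.9% → 8.4% |
| 0.5 | none | 2.0 | 0.497 | 0.474 | 4.6% | 6.7% → 2.8% |
| 0.5 | full | 1.5 | 0.498 | 0.385 | 22.7% | 15.8% → 4.5% |
| 0.5 | full | 2.0 | 0.502 | 0.447 | 11.0% | 6.7% → 1.3% |

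The rows without recovery show that regression to the mean alone, after selective retesting, costs about 4% to 7%. Recovery raises the loss to between 7% and 23%. Counting a patient as abnormal on any postbaseline value, as SAP 14.3 does for PCS, leaves the share at its scheduled figure in every row. That is so by construction, since a retest only follows a value above the threshold.

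**The case against.** A reader might infer that abnormal end-of-treatment values are erased from the safety record and that retests are always driven by abnormal findings. The documents do not support that reading.

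- Nothing is erased. Every postbaseline value counts towards PCS determinations and every assessment is listed. A clinically relevant abnormality is also an adverse event and so eligible for the treatment-emergent tables (Protocol 9.7.6.1, SAP 9.1). The exposure is largely confined to end-of-study means and any end-of-study categories, and chiefly to changes below PCS limits that were not judged clinically relevant.
- The reason for repeating an end-of-study assessment is not stated anywhere visible. The safety trigger is explicit for unscheduled and additional visits only; a repeat could equally follow an invalid sample. Adverse event follow-up may end at stabilization and does not by itself require a new laboratory or ECG record, and a later value may be unchanged or worse.
- An unscheduled visit before Visit 11 displaces nothing if Visit 11 is observed and no later value exists.
- The detailed laboratory, vital-sign and ECG analysis sections are not visible. If Day 21 is summarised by visit under Table 14.1-1, that row need not be affected.
- Safety analyses are descriptive (Protocol synopsis), and preferring the scheduled value has its own weakness: it may be the spurious reading that prompted the repeat.

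All of this stands and narrows the point. It does not answer two things. SAP 14.3 puts no time limit on the substituted value, and it is not reconciled with Table 14.1-1. The visits it draws on are, by the protocol's own wording, prompted by safety.

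**Conclusion.** The point holds in a limited form. SAP 14.3 as written allows a value taken after the final double-blind visit to become the end-of-study safety value, in patients selected partly because something was wrong. That mixes timepoints and can pull end-of-study means towards normal. The mixing and the conflict with SAP 14.1 need only a patient who has a later value. The pull towards normal also needs abnormal values to be retested more often than normal ones and to move back towards normal; this is plausible from the protocol but not stated for repeats.

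The size cannot be derived from the documents. The 4% to 23% loss is an illustration under assumed retest and recovery rates, neither a bound nor an estimate for this trial. It takes every value above the threshold as retested; less complete retesting would give a smaller loss. PCS counts, listings and adverse event tables are not affected. This is an inexpensive improvement to the SAP, not a threat to the trial's safety conclusions.

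**What to change.** In SAP 14.3, take the end-of-study safety value from the Day 21/ET window of Table 14.1-1: the scheduled Visit 11/ET assessment or, if that is missing, the last double-blind value. The fallback should be explicit, because Table 14.1-1 puts an ET visit before IndexB + 6 in an earlier window. Allow a repeat to replace the value only when the original sample or tracing was declared invalid. Keep later retest, unscheduled and follow-up values for PCS determinations, listings and the Day 28 or follow-up summary. State also that this rule prevails over the closest-to-target rule in SAP 14.1 for safety data, or that the two agree.

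The cost is a short text change and a programming flag, using data already collected. There are two downsides: end-of-study summaries may look slightly less favourable, and a spurious reading that was never declared invalid would stay in them.

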14.4 MISSING SEVERITY ASSESSMENT FOR ADVERSE EVENTS

If severity is missing for an AE that started before the date of the first dose of DB IP, an intensity of mild will be assigned. If severity is missing for an AE that started on or after the date of the first dose of DB IP, an intensity of severe will be assigned. The imputed values for severity assessment will be used for the incidence summary; the values will be shown as missing in the data listings.

14.5 MISSING CAUSAL RELATIONSHIP TO INVESTIGATIONAL PRODUCT FOR ADVERSE EVENTS

If the causal relationship to the IP is missing for an AE that started on or after the date of the first dose of DB IP, a causality of yes will be assigned. The imputed values for causal relationship to randomized treatment will be used for the incidence summary; the values will be shown as missing in the data listings.

14.6 MISSING DATE INFORMATION FOR ADVERSE EVENTS

The following imputation rules only apply to cases in which the start date for an AE is incomplete (ie, partly missing). If the patient did not receive any randomized dosing during the study, then the date of first dose of DB IP will be utilized for the purpose of imputation.

Missing month and day

- If the year of the incomplete start date is the same as the year of the first dose of randomized IP, the month and day of the first dose of randomized IP will be assigned to the missing fields.
- If the year of the incomplete start date is before the year of the first dose of randomized IP, *31 Dec* will be assigned to the missing fields.
- If the year of the incomplete start date is after the year of the first dose of randomized IP, *01 Jan* will be assigned to the missing fields.

Missing month only

- If only the month is missing, the day will be treated as missing and both the month and the day will be replaced according to the above procedure.

Missing day only

- If the month and year of the incomplete start date are the same as the month and year of the first dose of randomized IP, the day of the first dose of randomized IP will be assigned to the missing day.

- If either the year of the incomplete start date is before the year of the date of the first dose of randomized IP or if both years are the same but the month of the incomplete start date is before the month of the date of the first dose of randomized IP, the last day of the month will be assigned to the missing day.
- If either the year of the incomplete start date is after the year of the date of the first dose of randomized IP or if both years are the same but the month of the incomplete start date is after the month of the date of the first dose of randomized IP, the first day of the month will be assigned to the missing day.

If the stop date is complete and the imputed start date as above is after the stop date, the start date will be imputed by the stop date.

If the start date is completely missing and the stop date is complete, the following algorithm will be used to impute the start date:

- If the stop date is after the date of the first dose of randomized IP, the date of the first dose of randomized IP will be assigned to the missing start date.
- If the stop date is before the date of the first dose of randomized IP, the stop date will be assigned to the missing start date.

14.7 MISSING DATE INFORMATION FOR PRIOR OR CONCOMITANT MEDICATIONS

For prior or concomitant medications, including background ADT, incomplete (ie, partially missing) start dates and/or stop dates will be imputed. When the start date and the stop date are both incomplete for a patient, the start date will be imputed first. If the stop date is complete and the imputed start date is after the stop date, the start date will be imputed using the stop date. If the imputed stop date is before the start date (imputed or nonimputed start date), the start date will be the imputed stop date. If the patient did not receive any randomized dosing during the study, then the date of first dose of DB IP will be utilized for the purpose of imputation.

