6.0 DEMOGRAPHICS AND OTHER BASELINE CHARACTERISTICS

Demographic parameters and other baseline characteristics (eg, age, race, ethnicity, sex, weight, height, body mass index) will be summarized for all patients combined using the Enrolled Population, mITT Population, placebo responders of mITT Population, and placebo non-responders of mITT Population. An analogous analysis will be performed for baseline efficacy assessments.

Medical and surgical history, psychiatric history, previous treatment with psychotropic medication, and nondrug psychiatric treatment will be summarized by treatment group for the Safety Population.

The *World Health Organization (WHO) Drug Dictionary Enhanced* will be used to classify prior and concomitant medications by therapeutic class. *Prior medication* is defined as any medication taken before the date of the first dose of DB IP during the placebo lead-in period. *Concomitant medication* is defined as any medication taken on or after the date of the first dose of DB IP which is during the placebo lead-in period. If a medication started prior to the first dose of DB IP and continued into the placebo lead-in period, then this medication will be included in the analysis of prior and concomitant medications separately.

The number and percentage of patients with prior and concomitant medication use will be summarized by treatment group and Anatomical Therapeutic Chemical code for the Safety Population.

Multiple medications used by a patient in the same category will be counted only once in the summary tables. Concomitant medications started after the last visit of the randomized treatment period will not be summarized but will be included in the data listings.

Prior ADT treatment in the current episode, as recorded on ATRQ, will be summarized by frequency counts and percentages for patients who took each ADT in adequate dose and duration, total number of ADT taken at adequate dose and duration (ie., 1, 2, 3, or >3), and percentage of improvement reported (ie., $<25\%$, 25% to 49% , 50% to 75% , or $>75\%$).

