14.7.2 Incomplete Stop Date

The following rules will be applied to impute the missing numeric fields for an incomplete prior or concomitant medication stop date. If the imputed stop date is before the start date (imputed or nonimputed start date), the imputed stop date will be equal to the start date.

Missing month and day

[figure not shown]
- If the year of the incomplete stop date is the same as the year of the last dose of randomized IP, the month and day of the last dose of randomized IP will be assigned to the missing fields.
- If the year of the incomplete stop date is before the year of the last dose of randomized IP, *31 Dec* will be assigned to the missing fields.
- If the year of the incomplete stop date is after the year of the last dose of randomized IP, *01 Jan* will be assigned to the missing fields.

[figure not shown]
Missing month only

- If only the month is missing, the day will be treated as missing and both the month and the day will be replaced according to the above procedure.

Missing day only

- If the month and year of the incomplete stop date are the same as the month and year of the last dose of randomized IP, the day of the last dose of randomized IP will be assigned to the missing day.
- If either the year of the incomplete stop date is before the year of the date of the last dose of randomized IP or if both years are the same but the month of the incomplete stop date is before the month of the date of the last dose of randomized IP, the last day of the month will be assigned to the missing day.
- If either the year of the incomplete stop date is after the year of the date of the last dose of randomized IP or if both years are the same but the month of the incomplete stop date is after the month of the date of the last dose of randomized IP, the first day of the month will be assigned to the missing day.

[figure not shown]

RESERVED

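### SAP 14.7 and 14.7.2 correct the same date conflict in opposite directions, and 14.7 lets an imputed medication stop date overwrite a recorded start date

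*SAP*

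**What the plan says.** SAP 14.7 covers incomplete start and stop dates for prior and concomitant medications, including background ADT. It fixes the order of work: "When the start date and the stop date are both incomplete for a patient, the start date will be imputed first". It then gives a correction for an imputed stop date that falls before the start date, whether or not that start date was itself imputed: "the start date will be the imputed stop date".

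SAP 14.7.2, which holds the detailed rules for incomplete stop dates, opens with the same condition and ends differently: "the imputed stop date will be equal to the start date".

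SAP 6.0 makes the start date matter for reporting: "Concomitant medications started after the last visit of the randomized treatment period will not be summarized". Such drugs appear in the listings only. SAP 6.0 also separates prior from concomitant use at the first double-blind dose, which is given in the placebo lead-in.

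**The concern.** The condition is worded identically in the two sections, so neither is a special case of the other. SAP 14.7 keeps the imputed stop date and pulls the start date back to it. SAP 14.7.2 keeps the start date and pushes the imputed stop date forward. Two programmers working independently could each follow the SAP and produce different data sets.

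SAP 14.7 also names start dates that were not imputed. It therefore discards a date the site recorded in favor of one the SAP made up. That is out of line with the SAP's neighboring rules: in 14.6 and earlier in 14.7, where an imputed start falls after a complete stop date, only the imputed start is changed.

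At stake are the medication summary tables and the dates attached to background ADT records.

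**Working it through.** No figure in the plan needs reproducing, so the check applies the rules to example records.

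**Assumed dates (not from the documents, but following the SAP's Day 0, 7, 14 and 21 schedule).** First double-blind dose 1 March 2018; randomized doses 8 and 15 March; last randomized-period visit 22 March. The Day 28 target is 15 March + 14 days = 29 March.

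**Rules used.**
- *Start (SAP 14.7.1).* Only the year known and equal to the year of the first randomized dose: use that dose date. Month known and later than that dose's month: use the first of the month.
- *Stop (SAP 14.7.2).* Only the year known and equal to the year of the last randomized dose, or the same month and year as that dose: use that dose date. Earlier month: last day of the month. Later month: first day. Later year only: 1 January.

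| Record | Start recorded | Stop recorded | Start before correction | Imputed stop | Under 14.7 | Under 14.7.2 |
|---|---|---|---|---|---|---|
| A | 25 Mar 2018 | Mar 2018 | 25 Mar | 15 Mar | both 15 Mar: summarized | both 25 Mar: listed only |
| B | 2018 | Jan 2018 | 8 Mar | 31 Jan | both 31 Jan: prior only | both 8 Mar: concomitant only |
| C | Apr 2018 | 2018 | 1 Apr | 15 Mar | both 15 Mar: summarized | both 1 Apr: listed only |
| D | 25 Mar 2018 | Apr 2018 | 25 Mar | 1 Apr | no conflict | no conflict |
| E | 25 Mar 2018 | 2019 | 25 Mar | 1 Jan 2019 | no conflict | no conflict |
| F | 25 Apr 2018 | Apr 2018 | 25 Apr | 1 Apr | both 1 Apr: listed only | both 25 Apr: listed only |

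**What the records show.**
- A: SAP 14.7 overwrites a complete recorded start date, and the drug moves from the listing into the summary table.
- B: the choice of rule reverses prior and concomitant status. Protocol 9.7.4.1 draws the line at the first randomized dose (8 March here) and gives the same split. Here 14.7.2 is the rule that goes wrong, because it places a drug recorded as stopped in January in the treatment period.
- C: here 14.7 goes wrong, because it contradicts the recorded month of April.
- D and E: a start after the last visit with a partial stop date need not trigger the rule.
- F: the rule can be triggered without changing what is summarized.

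**Wider check, recorded starts only.** An assumed grid used 53 first-dose dates one week apart from 1 January 2018, 120 start days (60 before to 59 after the first dose) and 60 durations (0 to 59 days). The stop lacked either the day, or the month and day: 53 × 120 × 60 × 2 = 763,200 combinations. The two rules conflicted in 166,325. The choice changed whether the start fell after the last visit in 111,854 of these (111,854 / 166,325 = 67%). It changed prior status in none, because the imputed stop was never earlier than the last randomized dose. The grid shows what can happen; it does not estimate how often.

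**The case against.** The case for leaving this alone is that it is a drafting slip in a supporting derivation. That is fair as to weight: nothing here reaches the primary or key secondary MADRS analyses, the type I error or the sample size. It does not make the rule workable. The instruction to impute the start date first settles the order of imputation, not which correction applies. Both sentences are complete, so redaction or text extraction does not explain the conflict.

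A reader might infer more than the documents support:

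- *That every drug started after the last visit with a partial stop date changes period.* Records D, E and F show otherwise. For a recorded start, a change in summary status needs the imputed stop both to precede the start and to fall on or before the last randomized-period visit.
- *That 14.7 creates false concomitant use.* With a recorded start, as in record A, the drug is concomitant under both rules by the SAP 6.0 definition; only its place in the table or listing changes. Prior and concomitant status can reverse only when both dates are partial, as in record B.
- *That it creates false protocol deviations for background ADT.* Protocol 9.4.1 and 9.4.7.3 treat ADT changes during treatment and during follow-up differently, so a back-dated record could look odd. But SAP 5.1 leaves deviations to a separate specification that is not among the documents, and nothing shown derives them from imputed dates. Protocol 9.4.1 and 9.4.12 have ADT changes established by questioning and pill count, with changes entered in the eCRF.
- *That striking the sentence in 14.7 is a complete remedy.* Record B shows that it is not.

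A further objection is that such records lie at the edge of data collection. Record A does not: its start on 25 March falls before the planned Day 28 visit on 29 March.

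**Conclusion.** The point holds in a limited form. The two sections contradict each other on an identical condition, and 14.7 expressly allows a recorded start date to be replaced by an imputed stop date. The plan is wrong as written on this rule.

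For some records, the choice of rule moves a drug between the summary table and the listing. When both dates are partial, it can reverse prior and concomitant classification. I expect few records to be affected, but this is a judgment, since the documents do not say how many dates will be partial. The contradiction itself rests only on the text; the examples rest on the assumed dates. It is a minor correction, worth making before the medication data sets are programmed.

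**What to change.** Delete both correction sentences and put one rule in SAP 14.7, with a cross-reference from 14.7.2. The rule should say:

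1. A recorded date, or the recorded part of a partial date, is never overridden; only imputed parts move.
2. If the start date is fully recorded and the imputed stop date precedes it, the start date stands and the stop date is set equal to it.
3. If both dates are partly imputed, move whichever imputed part can move without contradicting a recorded part. In record B the start moves to 31 January. In record C the stop moves to 1 April.

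If the recorded parts themselves contradict each other, the record should go to data query. The existing rule for a complete stop date can stay, because it already moves only an imputed start. The cost is a sentence or two of SAP text and the matching line of program specification. No new data are needed and no efficacy analysis changes.
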